5.2.3.2. Management of PLD Extravasation

Discontinue PLD for burning or stinging sensation or other evidence indicating perivenous infiltration or extravasation. Manage confirmed or suspected extravasation as follows:

- Do not remove the needle until attempts are made to aspirate extravasated fluid;
- Do not flush the line;
- Avoid applying pressure to the site;
- Apply ice to the site intermittently for 15 min 4 times a day for 3 days;
- If the extravasation is in an extremity, elevate the extremity.

5.2.3.3. Avelumab Administration

Avelumab will be administered at 10 mg/kg on Day 1 and Day 15 of each 4-week cycle after all procedures/assessments have been completed as described in [Appendix 7](#). Avelumab may be administered up to 3 days before or after the scheduled day of administration of each cycle due to administrative reasons but there should not be less than 10 days between doses.

Avelumab will be administered as a 1-hour IV infusion once every 14 days.

In order to mitigate infusion-related reactions, patients must be premedicated with an antihistamine and paracetamol (acetaminophen) prior to the first 4 infusions of avelumab. Premedication will be administered for subsequent avelumab doses based upon clinical judgment and presence/severity of prior infusion reactions.

When avelumab is administered alone, premedications should be administered 30-60 minutes before the infusion. For Arm B patients, on visits when both PLD and avelumab are infused (every 4 weeks) avelumab will be infused after PLD. If premedication was administered prior to PLD, the decision whether to repeat pre-medication prior to avelumab is at the discretion of the investigator depending on the elapsed time and the half-life of corresponding premedication agent. The line should be flushed, according to local practice, between infusions, and a new administration set should be used for avelumab.

Sites should make every effort to target avelumab infusion timing to be as close to 1 hour as possible. However, given the variability of infusion pumps from site to site, time windows of minus 10 minutes and plus 20 minutes is permitted (ie, infusion time is 50-80 minutes). The exact duration of infusion should be recorded in both source documents and CRFs. Possible modifications of the infusion rate for the management of infusion-related reactions are described in [Section 5.2.6](#).

5.2.4. Treatment after Initial Evidence of Radiologic Disease Progression

Immunotherapeutic agents such as avelumab may produce antitumor effects by potentiating endogenous cancer-specific immune responses. The response patterns seen with such an approach may extend beyond the typical time course of responses seen with PLD and may manifest as a clinical response after an initial increase in tumor burden or even the appearance of new lesions.

If radiologic imaging shows progression, as assessed by the investigator, avelumab and PLD must be discontinued. For those patients who are on single-agent avelumab post-progression at the time of amendment approval, if they present with a subsequent scan showing disease progression, they must discontinue avelumab.

5.2.5. Food Requirements

Both study drugs may be administered without regard to food.

5.2.6. Recommended Dose Modifications

Every effort should be made to administer study treatment on the planned dose and schedule.

In the event of significant toxicity, dosing may be delayed and/or dose reduced as described below. In the event of multiple toxicities, dose modification should be based on the worst toxicity observed. Patients are to be instructed to notify Investigators at the first occurrence of any adverse symptom. In addition to dose modifications, investigators are encouraged to employ best supportive care according to local institutional clinical practices and according to the guidance for selected adverse events provided below.

If a PLD dose reduction is necessary, the PLD dose should be reduced initially to 30 mg/m², and then down to 20 mg/m² if a second dose reduction is required. Management of patients requiring more than 2 PLD dose reductions should be discussed with the Sponsor. Do not increase PLD dose after a prior dose reduction due to toxicity.

Table 4. Dose Modifications for PLD

Dose Level	PLD
Starting dose	40 mg/m ²
First dose reduction	30 mg/m ²
Second dose reduction	20 mg/m ²

For avelumab, no dose modifications are permitted in this study, but doses may be omitted based on persisting toxicity.

For patients on avelumab plus PLD combination treatment, PLD dose modifications as well as infusion omissions/ delays for PLD and/or avelumab may occur independently for the two drugs according to the guidance provided below for each individual drug and investigator’s medical judgment and will be reported in the CRF. If PLD is delayed by 1 week, avelumab should also be delayed by 1 week so that PLD and avelumab are administered together.

Some potential immune-related adverse events described with anti-PD-L1 drugs such as avelumab may overlap with PLD toxicities such as rash or diarrhea. For patients on avelumab or combination treatment with avelumab and PLD, any adverse event suspected to be immune-related should be managed according to the guidance for management of immune-related adverse events [Appendix 9: Management of Immune-related Adverse Events](#)). In case of a potential irAE, besides the management related to avelumab therapy, PLD doses may also be modified or interrupted based on the guidance provided for PLD toxicity management ([Section 5.2.8.2 PLD Infusion-related Reaction](#)), product labeling, and institutional guidelines according to investigator’s medical judgment.

Additional guidance for the management of avelumab-PLD combination is provided for Neutropenia and Thrombocytopenia ([Table 7](#)), Palmar-Plantar Erythrodysesthesia (Hand-Foot Syndrome) ([Table 9](#)), and Stomatitis ([Table 10](#)).

For toxicity management, the following tables/appendix should be referenced as appropriate.

Section 5.2.7.1	Avelumab: Adverse Drug Reactions Requiring Avelumab Discontinuation or Delays
Section 5.2.7.2.1	Avelumab: Special Precautions for Administration
Section 5.2.7.2 Table 5	Avelumab: Infusion Related Reactions
Section 5.2.7.2.2	Avelumab Severe Hypersensitivity Reactions and Flu like Symptoms
Appendix 9	Avelumab: Immune related Adverse Events
Table 7	PLD and avelumab PLD combination: Treatment Modification for Neutropenia and Thrombocytopenia
Section 5.2.8.2 Table 8	PLD: Infusion-Related Reactions (Hypersensitivity Reactions)
Table 9	PLD and avelumab PLD combination: Treatment modification for Palmar Plantar Erythrodysesthesia Hand Foot Syndrome, HFS)
Table 10	PLD and avelumab PLD combination: Treatment modification for Stomatitis

Table 11	PLD: Treatment Modification for other Non-Hematologic Toxicities and Laboratory Abnormalities
Section 5.2.9	All patients: Treatment modification for Left Ventricular Ejection Fraction Decreased
Figure 2	Tumor Lysis Syndrome

5.2.7. Guidelines for Avelumab Toxicity Management

5.2.7.1. Avelumab: Adverse Drug Reactions Requiring Discontinuation or Delays

The following adverse drug reactions (ADRs) require permanent treatment discontinuation of avelumab:

Any Grade 4 ADRs require permanent treatment discontinuation with avelumab except for single laboratory values out of normal range that are unlikely related to trial treatment as assessed by the Investigator, do not have any clinical correlate, and resolve within 7 days with adequate medical management.

Any Grade 3 ADRs require permanent treatment discontinuation of avelumab except for any of the following:

- Transient (≤ 6 hours) Grade 3 flu-like symptoms or fever, which are controlled with medical management.
- Transient (≤ 24 hours) Grade 3 fatigue, local reactions, headache, nausea, or emesis that resolve to Grade ≤ 1 .
- Transient Grade 3 diarrhea (≤ 24 hours) that resolves to Grade 1 or less without administration of steroids.
- Single laboratory values out of normal range (excluding Grade ≥ 3 liver function test increase) that are unlikely related to trial treatment according to the Investigator, do not have any clinical correlate, and resolve to Grade ≤ 1 within 7 days with adequate medical management.
- Tumor flare phenomena defined as local pain, irritation, or rash localized at sites of known or suspected tumor.
- Change in ECOG PS to ≥ 3 that resolves to ≤ 2 within 14 days (infusions should not be given on the following cycle, if the ECOG PS is ≥ 3 on the day of trial drug administration).

For any Grade 2 ADR, avelumab dosing should be managed as follows:

- If a Grade 2 ADR resolves to Grade ≤ 1 prior to the next scheduled dose, treatment may continue.
- If a Grade 2 ADR does not resolve to Grade ≤ 1 prior to the next scheduled dose, infusions should be withheld. If by the following scheduled infusion the event has not resolved to Grade 1, the patient should permanently discontinue treatment (except for hematological toxicities and hormone insufficiencies, that can be managed by replacement therapy; for these hormone insufficiencies, up to 2 subsequent doses may be omitted).
- Upon the second occurrence of the same Grade 2 ADR (except for hormone insufficiencies that can be managed by replacement therapy or hematologic toxicities) in the same patient, treatment with avelumab has to be permanently discontinued.

Avelumab infusion-related reactions, hypersensitivity reactions (Grades 1 to 4), tumor lysis syndrome, and irAEs should be handled according to guidelines in [Sections 5.2.7.2.1, 5.2.7.2.2, 5.2.10](#), respectively.

5.2.7.2. Avelumab: Infusion-related Reactions and Hypersensitivity Reactions

5.2.7.2.1. Avelumab: Special Precautions for Administration

In order to mitigate infusion-related reactions, patients must be premedicated with an antihistamine and paracetamol (acetaminophen) prior to the first 4 infusions of avelumab. Premedication will be administered for subsequent avelumab doses based upon clinical judgment and presence/severity of prior infusion reactions. See [Section 5.2.3.3](#) for instructions for patients on combination treatment.

As with all monoclonal antibody therapies, there is a risk of allergic reactions including anaphylactic shock. Avelumab should be administered in a setting that allows for immediate access to an intensive care unit or equivalent environment and administration of therapy for anaphylaxis, such as the ability to implement immediate resuscitation measures. Steroids (dexamethasone 10 mg), epinephrine (1:1,000 dilution), allergy medications (IV antihistamines), bronchodilators, or equivalents, and oxygen should be available for immediate access.

Infusion of avelumab will be stopped in case of Grade ≥ 2 infusion-related, allergic, or anaphylactic reactions. Following the first 4 avelumab infusions, patients must be observed for 2 hours post-infusion for potential infusion-related reactions. If no infusion reaction occurs in relation to the first 4 infusions, the post-infusion observation period may be discontinued. During this 2-hour observation period the patient should remain in a location where they can be observed by site staff. Vital sign measurements or other procedures are not required unless clinically indicated. If an allergic reaction occurs, the patient must be treated according to the best available medical practice. The emergency treatment of anaphylactic reactions according to the Working Group of the Resuscitation Council (United

Kingdom) can be found at <https://www.resus.org.uk/pages/reaction.pdf>. Patients should be instructed to report any delayed reactions to the Investigator immediately.

Table 5. Avelumab: Treatment Modifications for Symptoms of Infusion-related Reactions

NCI-CTCAE Grade	Treatment Modification for Avelumab
Grade 1 – mild Mild transient reaction; infusion interruption not indicated; intervention not indicated.	Decrease Avelumab infusion rate by 50% and monitor closely for any worsening.
Grade 2 – moderate Therapy or infusion interruption indicated but responds promptly to symptomatic treatment (eg, antihistamines, NSAIDs, narcotics, i.v. fluids); prophylactic medications indicated for ≤24 hours.	Stop Avelumab infusion. Resume infusion at 50% of previous rate once infusion-related reaction has resolved or decreased to at least Grade 1 in severity, and monitor closely for any worsening.
Grade 3 or Grade 4 – severe or life-threatening Grade 3: Prolonged (eg, not rapidly responsive to symptomatic medication and/or brief interruption of infusion); recurrence of symptoms following initial improvement; hospitalization indicated for clinical sequelae.	Stop the Avelumab infusion immediately and disconnect infusion tubing from the patient. Patients have to be withdrawn immediately from Avelumab treatment and must not receive any further Avelumab treatment.
Grade 4: Life-threatening consequences; urgent intervention indicated.	

i.v.=intravenous, NCI-CTCAE=National Cancer Institute-Common Terminology Criteria for Adverse Event, NSAIDs=nonsteroidal anti-inflammatory drugs.

Once the Avelumab infusion rate has been decreased by 50% due to an infusion-related reaction, it must remain decreased for all subsequent infusions.

Additional Modifications for Patients with Grade 2 Infusion-related Reactions

If, in the event of a Grade 2 infusion-related reaction that does not improve or worsens after implementation of the modifications indicated in Table 5 (including reducing the **infusion rate** by 50%), the investigator may consider treatment with corticosteroids and the infusion should be stopped for that day. At the next cycle, the investigator may consider the addition of H2-blocker antihistamines (eg, famotidine or ranitidine), in addition to the mandatory premedication. However, prophylactic steroids are NOT permitted. If the patient has a second infusion-related reaction ≥ Grade 2 on the slower infusion rate, with or without the addition of further medication to the mandatory premedication, the infusion should be stopped and the patient removed from avelumab treatment.

5.2.7.2.2. Avelumab: Severe Hypersensitivity Reactions and Flu-like Symptoms

If hypersensitivity reaction occurs, the patient must be treated according to the best available medical practice. A complete guideline for the emergency treatment of anaphylactic reactions according to the Working Group of the Resuscitation Council (United Kingdom) can be found at <https://www.resus.org.uk/pages/reaction.pdf>. Patients should be instructed to report any delayed reactions to the Investigator immediately.

Symptoms include impaired airway, decreased oxygen saturation (<92%), confusion, lethargy, hypotension, pale or clammy skin, and cyanosis. These symptoms can be managed with epinephrine injection and dexamethasone. Patients should be placed on monitor immediately, and the ICU should be alerted for possible transfer if required.

For prophylaxis of flu-like symptoms, 25 mg of indomethacin or comparable nonsteroidal anti-inflammatory drug (NSAID) dose (for example, ibuprofen 600 mg, naproxen sodium 500 mg) may be administered 2 hours before and 8 hours after the start of each dose of avelumab IV infusion. Alternative treatments for fever (for example, paracetamol) may be given to patients at the discretion of the investigator.

5.2.7.2.3. Avelumab: Immune-related Adverse Events

Because inhibition of PD-L1 stimulates the immune system, irAEs may occur. Treatment of irAEs is mainly dependent upon severity (NCI-CTCAE grade):

- Grades 1 to 2: treat symptomatically or with moderate dose steroids, more frequent monitoring.
- Grades 1 to 2 (persistent): manage similar to high grade AE (Grades 3 to 4).
- Grades 3 to 4: treat with high dose corticosteroids.

For patients receiving avelumab or avelumab-PLD combination, any event suspected to be immune-related should be managed according to the guidance for management of immune-related adverse events in this [Section 5.2.7.2.3](#) and [Appendix 9](#). In case of a potential irAE, besides the management related to avelumab therapy, PLD doses may also be modified or interrupted based on the guidance provided for PLD toxicity management in [Section 5.2.8.2](#), product labeling, and institutional guidelines according to investigator's best medical judgement.

Effective with Amendment 2, [Table 6](#) below is no longer applicable and has been replaced with [Appendix 9](#). Please follow [Appendix 9](#) for all management of immune-related adverse events.

Table 6. No Longer Applicable: Avelumab: Management of Immune-related Adverse Events

Gastrointestinal irAEs		
Severity of Diarrhea/Colitis (NCI-CTCAE v4.03)	Management	Follow-up
Grade 1 Diarrhea: <4 stools/day over Baseline Colitis: asymptomatic	Continue avelumab therapy Symptomatic treatment (eg, loperamide)	Close monitoring for worsening symptoms Educate patient to report worsening immediately If worsens: Treat as Grade 2 or 3/4
Grade 2 Diarrhea: 4 to 6 stools per day over Baseline; IV fluids indicated <24 hours; not interfering with ADL Colitis: abdominal pain; blood in stool	Delay avelumab therapy Symptomatic treatment	If improves to Grade 1: Resume avelumab therapy If persists >5 to 7 days or recur: 0.5 to 1.0 mg/kg/day methylprednisolone or equivalent When symptoms improve to Grade 1, taper steroids over at least 1 month, consider prophylactic antibiotics for opportunistic infections, and resume avelumab therapy per protocol. If worsens or persists >3 to 5 days with oral steroids: Treat as Grade 3 to 4
Grade 3 to 4 Diarrhea (Grade 3): ≥7 stools per day over Baseline; incontinence; IV fluids ≥24 hrs; interfering with ADL Colitis (Grade 3): severe abdominal pain, medical intervention indicated, peritoneal signs Grade 4: life-threatening, perforation	Discontinue avelumab therapy per protocol 1.0 to 2.0 mg/kg/day methylprednisolone IV or equivalent Add prophylactic antibiotics for opportunistic infections Consider lower endoscopy	If improves: Continue steroids until Grade 1, then taper over at least 1 month If persists >3 to 5 days, or recurs after improvement: Add infliximab 5 mg/kg (if no contraindication), Note: Infliximab should not be used in cases of perforation or sepsis
Dermatological irAEs		
Grade of Rash (NCI-CTCAE v4.03)	Management	Follow-up
Grades 1 to 2 Covering ≤30% body surface area	Symptomatic therapy (for example, antihistamines, topical steroids) Continue avelumab therapy	If persists >1 to 2 weeks or recurs: Consider skin biopsy Delay avelumab therapy Consider 0.5 to 1.0 mg/kg/day methylprednisolone IV or oral equivalent. Once improving, taper steroids over at least 1 month, consider prophylactic antibiotics for opportunistic infections, and resume avelumab therapy If worsens: Treat as Grades 3 to 4
Grades 3 to 4 Covering >30% body surface area; life threatening consequences	Delay or discontinue avelumab therapy Consider skin biopsy Dermatology consult	If improves to Grade 1: Taper steroids over at least 1 month and add prophylactic antibiotics for opportunistic infections

	1.0 to 2.0 mg/kg/day methylprednisolone IV or IV equivalent	Resume avelumab therapy
Pulmonary irAEs		
Grade of Pneumonitis (NCI-CTCAE v4.03)	Management	Follow-up
Grade 1 Radiographic changes only	Consider delay of avelumab therapy Monitor for symptoms every 2 to 3 days Consider Pulmonary and Infectious Disease consults	Re-image at least every 3 weeks If worsens: Treat as Grade 2 or Grade 3 to 4
Grade 2 Mild to moderate new symptoms	Delay avelumab therapy Pulmonary and Infectious Disease consults Monitor symptoms daily, consider hospitalization 1.0 mg/kg/day methyl-prednisolone IV or oral equivalent Consider bronchoscopy, lung biopsy	Re-image every 1 to 3 days If improves: When symptoms return to near Baseline, taper steroids over at least 1 month and then resume avelumab therapy and consider prophylactic antibiotics If not improving after 2 weeks or worsening: Treat as Grade 3 to 4
Grade of Pneumonitis (NCI-CTCAE v4.03)	Management	Follow-up
Grades 3 to 4 Severe new symptoms; New / worsening hypoxia; life-threatening	Discontinue avelumab therapy Hospitalize Pulmonary and Infectious Disease consults 2 to 4 mg/kg/day methylprednisolone IV or IV equivalent Add prophylactic antibiotics for opportunistic infections Consider bronchoscopy, lung biopsy	If improves to Baseline: Taper steroids over at least 6 weeks If not improving after 48 hours or worsening: Add additional immunosuppression (for example, infliximab, cyclophosphamide, IV immunoglobulin, or mycophenolate mofetil).
Hepatic irAEs		
Grade of Liver Test Elevation (NCI-CTCAE v4.03)	Management	Follow-up
Grade 1 Grade 1 AST or ALT > ULN to 3.0 x ULN and / or total bilirubin > ULN to 1.5 x ULN	Continue avelumab therapy	Continue liver function monitoring If worsens: Treat as Grades 2 or 3 to 4
Grade 2 AST or ALT >3.0 to ≤5 x ULN and / or total bilirubin >1.5 to ≤3 x ULN	Delay avelumab therapy Increase frequency of monitoring to every 3 days	If returns to Baseline: Resume routine monitoring, resume avelumab therapy If elevations persist >5 to 7 days or worsen: 0.5 to 1 mg/kg/day methylprednisolone or oral equivalent and when LFT returns to Grade 1 or Baseline, taper steroids over at least 1 month, consider prophylactic antibiotics for

		opportunistic infections, and resume avelumab therapy
Grades 3 to 4 AST or ALT >5 x ULN and / or total bilirubin >3 x ULN	Discontinue avelumab therapy Increase frequency of monitoring to every 1 to 2 days 1.0 to 2.0 mg/kg/day methylprednisolone IV or IV equivalent Add prophylactic antibiotics for opportunistic infections Consult gastroenterologist Consider obtaining MRI/CT scan of liver and liver biopsy if clinically warranted	If returns to Grade 2: Taper steroids over at least 1 month If does not improve in >3 to 5 days, worsens or rebounds: Add mycophenolate mofetil 1 gram (g) twice daily If no response within an additional 3 to 5 days, consider other immunosuppressants per local guidelines.
Cardiac irAEs		
Myocarditis	Management	Follow-up
New onset of cardiac signs or symptoms and / or new laboratory cardiac biomarker elevations (eg, troponin, CK-MB, BNP) or cardiac imaging abnormalities suggestive of myocarditis.	Withhold avelumab therapy Hospitalize in the presence of life threatening cardiac decompensation, consider transfer to a facility experienced in advanced heart failure and arrhythmia management Cardiology consult to establish etiology and rule out immune-mediated myocarditis. Guideline based supportive treatment as per cardiology consult.* Consider myocardial biopsy if recommended per cardiology consult.	If symptoms improve and immune-mediated etiology is ruled out, re-start avelumab therapy. If symptoms do not improve/worsen, viral myocarditis is excluded, and immune mediated etiology is suspected or confirmed following cardiology consult, manage as immune-mediated myocarditis.
Immune-mediated myocarditis	Permanently discontinue avelumab. Guideline based supportive treatment as appropriate as per cardiology consult.* Methylprednisolone 1 to 2 mg/kg/day	Once improving, taper steroids over at least 1 month and add prophylactic antibiotics for opportunistic infections. If no improvement or worsening, consider additional immunosuppressants (eg, azathioprine, cyclosporine A)
*Local guidelines, or eg. ESC or AHA guidelines ESC guidelines website: https://www.escardio.org/Guidelines/Clinical-Practice-Guidelines AHA guidelines website: http://professional.heart.org/professional/GuidelinesStatements/searchresults.jsp?q=&y=&t=1001		
Endocrine irAEs		
Endocrine Disorder	Management	Follow-up
Asymptomatic TSH abnormality	Continue avelumab therapy If TSH <0.5 x LLN, or TSH >2 x ULN, or consistently out of range in 2 subsequent measurements: include T4 at subsequent cycles as clinically indicated; consider endocrinology consult	

Symptomatic endocrinopathy	Evaluate endocrine function Consider pituitary scan Symptomatic with abnormal lab / pituitary scan: Delay avelumab therapy 1 to 2 mg/kg/day methylprednisolone IV or by mouth equivalent Initiate appropriate hormone therapy No abnormal lab/pituitary MRI scan but symptoms persist: Repeat labs in 1 to 3 weeks/MRI in 1 month	If improves (with or without hormone replacement): Taper steroids over at least 1 month and consider prophylactic antibiotics for opportunistic infections Resume avelumab therapy Patients with adrenal insufficiency may need to continue steroids with mineralocorticoid component.
Suspicion of adrenal crisis (for example, severe dehydration, hypotension, shock out of proportion to current illness)	Delay or discontinue avelumab therapy Rule out sepsis Stress dose of IV steroids with mineralocorticoid activity IV fluids Consult endocrinologist If adrenal crisis ruled out, then treat as above for symptomatic endocrinopathy	

ADL=activities of daily living, ALT=alanine aminotransferase, AST=aspartate aminotransferase, CT=computed tomography; irAE=immune-related adverse event, IV=intravenous, LFT=liver function test, LLN=lower limit of normal, MRI=magnetic resonance imaging, NCI-CTCAE=National Cancer Institute-Common Terminology Criteria for Adverse Event, anti-inflammatory drugs, T4=free thyroxine, TSH=thyroid-stimulating hormone, ULN=upper limit of normal.

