7.1.2. Adverse Events

7.1.2.1. Adverse Events of Special Interest for Avelumab

- Any AE that is suspected to be a potential irAE is considered an AE of special interest (AESI). Specific guidance for the management of immune-related AEs is provided in [Section 5.2.7.2.3](#), [Appendix 9](#) Avelumab Management of Immune-related Adverse Events. AESIs are reported according to the general AE reporting rules specified in [Section 8.2](#).

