Appendix 9. Management of Immune-related Adverse Events

Gastrointestinal irAEs		
Severity of Diarrhea/Colitis (NCI-CTCAE v4)	Initial Management	Follow-up Management
Grade 1 Diarrhea: <4 stools/day over Baseline Colitis: asymptomatic	Continue avelumab therapy Symptomatic treatment (eg, loperamide)	Close monitoring for worsening symptoms Educate subject to report worsening immediately If worsens: Treat as Grade 2, 3 or 4
Grade 2 Diarrhea: 4 to 6 stools per day over Baseline; IV fluids indicated (<24 hours; not interfering with ADL) Colitis: abdominal pain; blood in stool	Withhold avelumab therapy Symptomatic treatment	If improves to Grade ≤ 1 : Resume avelumab therapy If persists >5-7 days or recurs: Treat as Grade 3 or 4
Grade 3 to 4 Diarrhea (Grade 3): ≥ 7 stools per day over Baseline; incontinence; IV fluids ≥ 24 h; interfering with ADL Colitis (Grade 3): severe abdominal pain, medical intervention indicated, peritoneal signs Grade 4: life-threatening, perforation	Withhold avelumab for Grade 3 Permanently discontinue avelumab for Grade 4 or recurrent Grade 3 1.0 to 2.0 mg/kg/day prednisone IV or equivalent Add prophylactic antibiotics for opportunistic infections Consider lower endoscopy	If improves: Continue steroids until Grade ≤ 1 , then taper over at least 1 month; resume avelumab therapy following steroids taper (for initial Grade 3) If worsens, persists >3 to 5 days, or recurs after improvement: Add infliximab 5 mg/kg (if no contraindication). Note: infliximab should not be used in cases of perforation or sepsis

Dermatological irAEs		
Grade of Rash (NCI-CTCAE v4)	Initial Management	Follow-up Management
Grade 1 to 2 Covering \leq 30% body surface area	Continue avelumab therapy Symptomatic therapy (for example, antihistamines, topical steroids)	If Grade 2 persists $>$ 1 to 2 weeks or recurs: Withhold avelumab therapy Consider skin biopsy Consider 0.5-1.0 mg/kg/day prednisone or equivalent. Once improving, taper steroids over at least 1 month, consider prophylactic antibiotics for opportunistic infections, and resume avelumab therapy following steroids taper. If worsens: Treat as Grade 3 to 4

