New onset of cardiac signs or symptoms and/or new laboratory cardiac biomarker elevations (eg, troponin, CK-MB, BNP) or cardiac imaging abnormalities suggestive of myocarditis	Withhold avelumab therapy Hospitalize In the presence of life threatening cardiac decompensation, consider transfer to a facility experienced in advanced heart failure and arrhythmia management Cardiology consult to establish etiology and rule-out immune-mediated myocarditis Guideline based supportive treatment as per cardiology consult* Consider myocardial biopsy if	If symptoms improve and immune-mediated etiology is ruled out, re-start avelumab therapy If symptoms do not improve/worsen, viral myocarditis is excluded, and immune-mediated etiology is suspected or confirmed following cardiology consult, manage as immune-mediated myocarditis

	recommended per cardiology consult.	
Immune-mediated myocarditis	
Permanently discontinue avelumab
 
Guideline based supportive treatment as appropriate as per cardiology consult*
 
1.0 to 2.0 mg/kg/day prednisone or equivalent
 
Add prophylactic antibiotics for opportunistic infections
	
Once improving, taper steroids over at least 1 month
 
If no improvement or worsening, consider additional immunosuppressants (eg, azathioprine, cyclosporine A)

*Local guidelines, or eg, ESC or AHA guidelines
 
ESC guidelines website: https://www.escardio.org/Guidelines/Clinical-Practice-Guidelines
 
AHA guidelines website: http://professional.heart.org/professional/GuidelinesStatements/searchresults.jsp?q=&y=&t=1001
		
Endocrine irAEs		
Endocrine Disorder	Initial Management	Follow-up Management
Grade 1 or Grade 2 endocrinopathies (hypothyroidism, hyperthyroidism, adrenal insufficiency, type I diabetes mellitus)	
Continue avelumab therapy
 
Endocrinology consult if needed
 
Start thyroid hormone replacement therapy (for hypothyroidism), anti-thyroid treatment (for hyperthyroidism), corticosteroids (for adrenal insufficiency) or insulin (for Type I diabetes mellitus) as appropriate
 
Rule-out secondary endocrinopathies (ie, hypopituitarism/hypophysitis)
	
Continue hormone replacement/suppression and monitoring of endocrine function as appropriate

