9. APPENDICES

Appendix 1. Immune-Related Adverse Events

The MedDRA PTs and clusters for irAEs are defined in the Safety Review Plan (SRP) for avelumab.

Immune-related AEs (irAEs) will be programmatically identified as outlined in Table 16. This case definition is hierarchical, ie, each step is only checked for patients and events that have already met the prior step.

Table 16. Case Definition for irAEs

Step	Selection Criteria	Additional Notes
1	Event selected based on a list of pre-specified MedDRA PTs within clusters. These are included in the SRP as Tier1 events (Immune-mediated xxxx). If AE matches the list then it is in for the next step	
2	AE onset during 1 st study drug administration or anytime thereafter through 90 days after last dose of study treatment.	This is regardless of start of new anti-cancer drug therapy and regardless of TEAE classifications
3	Answer in the AE eCRF page to ‘Was another treatment given because of the occurrence of the event’ is ‘YES’	
4	AE treated with corticosteroids or other immunosuppressant therapy. For endocrinopathies only: AE required hormone replacement	Look in the conmed pages for AE identifiers that match the AEs from Step 3. For each of such AEs if A) OR B) below are met then the AE is in for the next step A) conmed ATC code is in (H02A, H02B, H02C, D07, A01AC, S01BA, S01BB, L04AA, L04AB, L04AC, L04AD, L04AX) and AE PT is in any of the irAE clusters. B) conmed ATC code is in (H03A, H03B) and AE PT is in one of the irAE clusters associated with “Immune-mediated endocrinopathies”

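### For some immune-related events the general steroid rules in Protocol Section 5.2.7.2.3 contradict Appendix 9, and the protocol gives two answers on which text governs

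*Protocol*

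**What the plan says.** Protocol Section 5.2.7.2.3 opens with the statement "Treatment of irAEs is mainly dependent upon severity (NCI-CTCAE grade") and gives three rules:

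- The starting rule for the lower grades is "Grades 1 to 2: treat symptomatically or with moderate dose steroids, more frequent monitoring".
- If such an event does not resolve, the rule becomes "Grades 1 to 2 (persistent): manage similar to high grade AE (Grades 3 to 4").
- The rule for the most severe events is "Grades 3 to 4: treat with high dose corticosteroids".

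None names an organ, gives a dose in mg/kg or says how long an event must last to be persistent. The next paragraph requires suspected irAEs to be managed under that section together with Appendix 9. The paragraph after that retires Table 6 as of Amendment 2 and sends all irAE management to Appendix 9.

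Section 7.1.2.1 points to both sources, Section 5.2.7.2.3 and Appendix 9, after the words "Specific guidance for the management of immune-related AEs is provided in". Section 5.2.6, in its text and in its look-up table, cites Appendix 9 alone.

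Appendix 9 is organised by organ and grade. For Grade 1 or 2 endocrinopathy it continues avelumab and says "Start thyroid hormone replacement therapy (for hypothyroidism), anti-thyroid treatment (for hyperthyroidism), corticosteroids (for adrenal insufficiency) or insulin (for Type I diabetes mellitus) as appropriate". For Grade 2 rash that persists or recurs it says "Consider 0.5-1.0 mg/kg/day prednisone or equivalent".

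**The concern.** A site that treats an irAE has two current instructions in the same protocol, one general and one specific to the organ. For some events they lead to different actions, so whether a patient receives systemic corticosteroids, and at what dose, can depend on which paragraph is read. Steroid exposure is not neutral in this trial: Section 5.4.6 says immunosuppressives such as steroids may counteract the intended benefit. The same section also says that short-term use may not compromise outcomes, and it allows steroids per site standard of care.

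The text still directs care. Amendment 2 keeps the study open so that patients remaining in Arms A and B can continue avelumab.

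**Working it through.** No sample size, alpha, power or event count enters this point, so the check is a comparison of texts.

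**Step 1. Are the general rules in force?** Yes. The Amendment 2 notice in Section 5.2.7.2.3 withdraws only Table 6. The paragraph that follows the rules names Appendix 9, so it belongs to the current text, and it refers sites back to the section that contains the rules.

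**Step 2. Where do the rules and Appendix 9 differ?**

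| Event | General rule in 5.2.7.2.3 | Appendix 9 |
|---|---|---|
| Grade 3-4 hypothyroidism, hyperthyroidism, type I diabetes | High dose corticosteroids | Thyroid hormone, anti-thyroid drug or insulin; corticosteroids named only for adrenal insufficiency |
| Persistent Grade 1-2 endocrinopathy | Manage as Grade 3-4 | Avelumab continues, with ongoing replacement or suppression and monitoring; no step-up for persistence |
| Persistent Grade 2 rash | Manage as Grade 3-4 | 0.5-1.0 mg/kg/day to be considered; Grade 3-4 rash has 1.0-2.0 mg/kg/day |
| Persistent Grade 1 GI, pulmonary, hepatic, renal | Manage as Grade 3-4 | Step-up only if the event worsens |

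The first row does not depend on how high dose or persistent is defined, because Appendix 9 names no corticosteroid for those three conditions. The second row stands even if managing as Grade 3-4 means no more than using the Grade 3-4 row of Appendix 9: that row withholds avelumab, while the Grade 1-2 row continues it. In the third row the two dose ranges meet only at 1.0 mg/kg/day, and the lower range is optional.

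**Step 3. Where do they agree?**

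- Grade 3-4 events outside the endocrine group: Appendix 9 gives 1.0-2.0 mg/kg/day in all six graded categories (GI, skin, lung, liver, kidney, other) and for immune-mediated myocarditis. Reading that range as high dose is an assumption, since Section 5.2.7.2.3 gives no figure; it is the highest steroid range in Appendix 9. On that reading the conflicts are 0 of 6.
- Persistent Grade 2 diarrhea/colitis and hepatic events: Appendix 9 also moves these to Grade 3-4 management.

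**Step 4. How far does the endocrine conflict reach?** Appendix 9 names four endocrinopathies plus hypophysitis. Hypothyroidism, hyperthyroidism and type I diabetes have no steroid at any grade. Adrenal insufficiency has corticosteroids, and hypophysitis has 1-2 mg/kg/day when symptoms are moderate or worse or the MRI is abnormal. That makes 3 of 5 endocrine entries without a steroid.

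**Step 5. Which text governs?** Section 5.2.7.2.3 names both sources in one paragraph and Appendix 9 for all management in the next. Section 7.1.2.1 supports the first statement; Section 5.2.6 supports the second.

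**The case against.** The strongest reply is that the protocol already settles the matter. The sentence written for Amendment 2 sends all irAE management to Appendix 9, Section 5.2.6 agrees twice, and the word mainly marks the severity rules as a general introduction to a table by organ. The rules did not match the superseded Table 6 row by row either: it gave 0.5-1.0 mg/kg/day for persistent Grade 2 diarrhea and hepatic events against 1.0-2.0 for Grade 3-4. This reply has weight. A reader should not infer that the protocol simply orders sites to follow both texts, or that Amendment 2 created the mismatch. What it does not remove is a current paragraph in the same section, and a second reference in Section 7.1.2.1, that still make the rules part of the guidance. The rules themselves are worded as instructions.

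Three stronger readings are tempting, and the documents do not support them.

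- **A count of affected patients.** One could apply the ovarian cohort's hypothyroidism rate, 5/75 = 6.7%, to the two avelumab arms, 550 x 2/3 = about 367, and obtain about 24 patients. But Appendix 9 took effect only with Amendment 2, after the final analysis, for patients still on treatment. The 367 is the planned number over the whole study, and nothing shows how many cases would persist.
- **A distorted irAE rate.** SAP Appendix 1, Table 16, Step 4 requires "AE treated with corticosteroids or other immunosuppressant therapy" for an event to count. Protocol Section 9 says the final analysis was already complete, so this conflict could not have driven its irAE rate. Hypothyroidism also qualifies through hormone replacement, and medical review may add cases.
- **Further conflicting rows.** For Grade 2 pneumonitis, creatinine increase and other irAEs, Appendix 9 starts at 1.0-2.0 mg/kg/day where the general rule allows symptomatic treatment or moderate dose steroids. Because moderate and high are not defined, these rows cannot be called contradictions.

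**Conclusion.** The point holds in a limited form. The general rules contradict Appendix 9 for the four groups of events in the table, and the protocol states in two ways which text governs. The consequence is possible inconsistency in steroid management among patients still on avelumab under Amendment 2. The documents do not give that number, so no patient count can be attached.

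The agreement found outside the endocrine group rests on reading 1.0-2.0 mg/kg/day as high dose. The conflict for Grade 3-4 hypothyroidism, hyperthyroidism and type I diabetes needs no such assumption. The primary analyses and the design figures are untouched. The point is worth acting on because the text directs current care and the correction is small.

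**What to change.** Reconcile the severity rules in Section 5.2.7.2.3 with Appendix 9, so that no event has two different instructions, and make Sections 5.2.7.2.3 and 7.1.2.1 name the same single governing source. Which text is changed, and which instruction is clinically right for each event, is for the sponsor's clinical team. The cost is wording in one section and one cross-reference; no procedure or data collection is added.
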